9.2.3. Analysis of the Primary Endpoints

The co-primary endpoints will be analyzed using the (Cochran-Mantel-Haenszel) test adjusted by baseline disease severity group (moderate and severe) and for a given dose both must achieve statistical significance to meet the primary objective. The difference between each active group and the placebo group in the proportion of subjects achieving IGA response (similarly for EASI-75) along with its 95% confidence interval (using the normal approximation for the difference in binomial proportions) will be reported. If a subject withdraws from the study, then this subject will be counted as non-responder for endpoints after withdrawal.

Additional secondary analyses will utilize missing at random (MAR) and missing not at random (MNAR) approaches. Missing observations will be multiply imputed using a tipping point analysis to estimate the treatment effect under the assumption that the missing data mechanism is MAR or more generally, is MNAR. A longitudinal logit-normal mixed model will be fit using only the observed data. Under the MAR framework, imputations will be based on the posterior predictive probability of response obtained from the posterior distribution under the mixed model. Under an MNAR framework, imputations for the active treatment groups will be based on a linear combination of the posterior predictive probability of response for the active group and the placebo group. For each such completed dataset, the estimates of the proportions and Cochran-Mantel-Haenszel (CMH)-weighted difference of proportions between each active dose group and placebo will be obtained and Rubin's rule will be used to combine the multiple estimates and standard errors across the imputed datasets and provide p-values.

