5.3.1. Binary Endpoints

For binary endpoints analyzed at each scheduled visit separately, visit windows (see [Appendix 2](#)) will be used to map all observed data into nominal visits. After mapping, for subjects who drop out for any reason, any data will be defined as “non-responsive” at all subsequent visits after the last observed value; for other subjects, any observations missing intermittently (including baseline values) will be considered missing completely at random (MCAR) and will remain missing in the analysis.

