6.3. Key Secondary Efficacy Endpoints

6.3.1. Week 2 NRS4 for severity Response

- Summary: Proportion of subjects with NRS4 for severity response at Week 2; Week 2 NRS value is based on visit window ([Appendix 2](#));
- Population: Subjects from the FAS with a baseline NRS score for severity ≥ 4 ;
- Statistical Method: CMH and normal approximation in [Section 5.2.1](#). In addition to comparisons versus placebo, tests of hypotheses will also be performed (with p-values reported) for comparing this endpoint between PF-04965842 200 mg QD and dupilumab as well as between PF-04965842 100 mg QD and dupilumab;
- Missing Data: Missing data arising due to subject dropout are considered “non-response” (see [Section 5.3.1](#)).

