Appendix 2. Definition and Use of Data Cut and Visit Windows in Reporting

For both the Week 16 Analysis and End of Study Analysis, a data cut at Week 16 drug dispensing visit will apply to each subject before the windowing. Only data from up to and including the Data Cut will be used for the Week 16 Analysis. Only data from after the Data Cut will be used for the End of Study Analysis. If a subject withdrew from the study and no drug was dispensed at Week 16, all available data for that subject will be included in the Week 16 Analysis.

Week 16 Analysis:

Visit Label	Target Day	Definition [Day window]
Screening		Days -28 to Day -1
Baseline	Day 1, Baseline	Day 1
Week 2	15	Days 2 to 22
Week 4	29	Days 23 to 43
Week 8	57	Days 44 to 71
Week 12	85	Days 72 to 99
Week 16	113	Days 100 to 120

End of Study Analysis:

Visit Label	Target Day	Definition [Day window]
Week 18	127	Days 121 to 134
Week 20	141	Days 135 to 155
Follow Up/End of Study		
Week 24	-	Days 156 to -

Visit windows will be used for efficacy variables, and for any safety data that display or summarize by study visit. For other endpoints (eg, ECG, vital signs), visit windows will be applied for summary statistics by study visits if required.

For the lab values, if the calculated study day for the labelled baseline visit is not study Day 1 but falls within 28 days before the start of the study dosing, then that data should be used for the baseline instead of leaving baseline missing.

For the other values, if the calculated study day for the labelled baseline visit is not study Day 1, but falls before the start of the study dosing, then that data should be used for the baseline instead of leaving baseline missing.

Observations on the actual day will be used to analyze Days 2-15 Pruritus NRS. Weeks 2, 4, 8, 16 Pruritus NRS will be based on the windowing method.

If two or more visits fall into the same window, keep the one closest to the Target Day. If two visits are equaled distant from the Target Day in absolute value, the later visit should be used.

Safety analysis may follow CaPS.

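### Read literally, the SAP lets a subject who leaves the study before Week 2 count as a Week 2 itch responder, whereas the protocol counts that subject as a non-responder; separately, a late Week 16 assessment is used by neither analysis

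*SAP*

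**What the plan says.** Week 2 NRS4 (a fall of at least 4 points in Pruritus NRS severity) is a key secondary endpoint. SAP 6.3.1 states "Week 2 NRS value is based on visit window". Appendix 2 sets the Week 2 window at Days 2 to 22 with target Day 15, keeps the record closest to the target, and confirms "Weeks 2, 4, 8, 16 Pruritus NRS will be based on the windowing method". Protocol 6.1 has the score entered in the eDiary every day from Day 1 to Day 15.

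SAP 5.3.1 fixes the order of operations. Visit windows "will be used to map all observed data into nominal visits". After that, "for subjects who drop out for any reason", data are set to non-response "at all subsequent visits after the last observed value". For a subject who withdrew with no Week 16 dispensing, Appendix 2 adds that "all available data for that subject will be included in the Week 16 Analysis".

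Protocol 9.2.3 reads: "If a subject withdraws from the study, then this subject will be counted as non-responder for endpoints after withdrawal". Protocol 9.2.4 applies the co-primary method to the key secondary proportions, and names the 4-point itch response among them.

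For the daily tests Appendix 2 uses a different basis: "Observations on the actual day will be used to analyze Days 2-15 Pruritus NRS".

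The Week 16 window is Days 100 to 120. The Week 16 Analysis uses data up to and including the Week 16 drug-dispensing visit (the Data Cut), and the End of Study Analysis uses only data after it.

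**The concern.** The Week 2 window opens on Day 2 and has no minimum duration of treatment, so an early diary entry is enough to fill it. For a subject who has left the study, that entry then counts as an observed Week 2 result, and non-response starts only at Week 4. The protocol reads more naturally the other way: the Week 2 visit is Day 15 ±1, so a Week 2 endpoint comes after a Day 8 withdrawal.

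According to SAP 6, p-values against dupilumab are given only for Week 2 NRS4 and for the Days 2-15 tests, and SAP 5.1 places the daily tests in a separate family. The dupilumab claim under familywise control therefore rests on Week 2 NRS4. Two defensible readings of one subject's outcome should not be left open there.

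The same appendix has an unrelated gap at Week 16, which touches the other two key secondary endpoints, IGA and EASI-75.

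**Working it through.** **1. One subject under each rule.** Suppose the last diary entry and study withdrawal are both on Day 8, with a fall of at least 4 points.

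| Rule | Step | Result |
|---|---|---|
| SAP 5.3.1, 6.3.1, Appendix 2 | Day 8 lies in Days 2-22 and is the entry closest to Day 15; non-response starts at Week 4 | Week 2 responder |
| Protocol 9.2.3 with 9.2.4 | Withdrawn before the Week 2 visit | Week 2 non-responder |
| SAP Day 15 test | Actual day; no Day 15 value; dropout | Day 15 non-responder |

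Every diary day from 2 to 15 maps to Week 2, so the result does not depend on choosing Day 8.

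**2. The plan's own figure.** Protocol 9.1 gives at least 92% power for 33% versus 18% with 200 per arm. With pooled standard error √(2×0.255×0.745/200) = 0.0436 and unpooled 0.0429, power at two-sided 5% is Φ((0.15 − 1.960×0.0436)/0.0429) = 93.4%, which agrees. At 2.5%, the level at which Sequence A starts, it is 88.8%. The steps below use 2.5%.

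**3. Distance to the threshold.** CMH statistic with one stratum (the severity split is not given), 36/200 on dupilumab (18%):
- 55/200 on PF-04965842: expected 45.5, variance 40000×91×309/(400²×399) = 17.62; (9.5)²/17.62 = 5.12, p = 0.0236.
- 54/200: expected 45, variance 40000×90×310/(400²×399) = 17.48; 9²/17.48 = 4.63, p = 0.0314.

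One subject separates significance from non-significance at that point.

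**4. Possible size.** Let m be the share of an arm that withdraws before Day 14 with an earlier entry, and r the share of those meeting NRS4 at that entry. Moving from the protocol rule to the SAP rule changes the PF-04965842 minus dupilumab difference by m_PF×r_PF − m_D×r_D. The documents give neither m nor r. Assumed ranges: m from 0 to 5%, r from 0 to 50%.

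| PF (m, r) | Dupilumab (m, r) | Shift, points |
|---|---|---|
| 2%, 18% | 2%, 8% | 0.36 − 0.16 = +0.20 |
| 5%, 18% | 5%, 8% | 0.90 − 0.40 = +0.50 |
| 2%, 18% | 5%, 18% | 0.36 − 0.90 = −0.54 |
| 5%, 18% | 2%, 18% | 0.90 − 0.36 = +0.54 |
| 3%, 18% | 3%, 18% | 0 |
| 5%, 50% | none | +2.50 |
| none | 5%, 50% | −2.50 |

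In the mid-range rows no arm gains more than 1.8 subjects of 200 (0.90%).

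**5. Effect on the chance of significance.** Exact binomial enumeration with the step 3 statistic at 2.5%, each scenario's shift placed on the arms it belongs to:
- No shift, 33% v 18%: 89.1%.
- −0.54, 33.36% v 18.90%: 85.9%.
- +0.54, 33.90% v 18.36%: 90.8%.
- −2.50, 33% v 20.5%: 72.4%.
- +2.50, 35.5% v 18%: 96.1%.

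**6. Week 16.** Take a dispensing visit on Day 121. The assessment is within the Data Cut, so it is excluded from the End of Study Analysis; it is past Day 120, so no Week 16 Analysis window holds it. Unless another assessment falls in Days 100-120, this continuing subject's Week 16 IGA and EASI-75 are missing, and SAP 5.3.1 leaves intermittent missing values missing. Day 121 is 8 days after the Day 113 target, against a visit window of ±3 days, so few such cases are expected.

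**The case against.** The best counter-argument is that the protocol does not say which observation supplies Week 2 and leaves detail to the SAP. If the SAP defines Week 2 by a window, a value recorded before withdrawal might be called an endpoint reached before withdrawal. In addition, the Appendix 2 rule for choosing within a window speaks of visits, so home diary entries might be meant only for the daily tests. The schedule-of-activities footnote for this scale is not visible in the public text, so some collection detail is unseen. These points stand far enough to limit confidence to moderate. They do not remove the problem, because SAP 5.3.1 refers to all observed data and nothing in the text keeps diary entries out of the Week 2 window.

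Several stronger readings are tempting, and the documents do not support them:
- *An improper change to the protocol.* Protocol 9 and SAP 2 let the SAP modify the protocol and require an amendment only for major changes to the primary endpoints. NRS4 is key secondary, and the SAP's Table 1 records changes between SAP versions, not departures from the protocol. No rule is broken by silence.
- *A contradiction within the SAP.* The non-response entries in 6.3.1 and Appendix 1 cover missing data, and here the value is not missing. Week 2 and Day 15 are deliberately separate tests, so a difference between them is not in itself an error.
- *A bias towards PF-04965842.* No early withdrawal or early response rates are given, so the direction is unknown.
- *All early treatment stops are affected.* Under protocol 6.4, subjects who stop treatment remain in the study. The conflict with 9.2.3 concerns study withdrawal only.

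**Conclusion.** The concern holds as a minor point with moderate confidence. On the literal text, SAP 5.3.1 with Appendix 2 and protocol 9.2.3 with 9.2.4 classify the same early withdrawal in opposite ways for a key secondary endpoint, and neither document reconciles them.

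Under the assumed rates the difference between arms moves by about half a point in mid-range cases and by 2.5 points at the extremes, in either direction. The extremes require 10 early withdrawals in one arm, half of them responders, and no counted responders among early withdrawals in the other. That one subject can decide a result exactly at the threshold is true of any counting rule; it is a reason to settle this rule beforehand, not evidence of a large effect.

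The Week 16 gap holds independently and should affect few subjects.

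**What to change.** Before unblinding for the Week 16 Analysis:

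- In SAP 5.3.1 and 6.3.1, state that a subject who withdraws or is lost to follow-up without attending the Week 2 visit, and who has no NRS value on or after Day 14, is a Week 2 NRS4 non-responder. Judge this by the last assessment or contact, not by the date on which the subject is declared withdrawn or lost. Protocol 6.4 requires repeated contact attempts and a registered letter before loss is declared, so a subject last heard from on Day 5 could be classified as lost only after Day 14.
- Keep the nearest-to-Day-15 rule within Days 2-22 for all other subjects.
- In Appendix 2, assign the assessment made at the Week 16 dispensing visit to Week 16 for subjects dispensed drug at that visit, with a stated upper day limit for late visits. Keep the Day 120 limit for subjects with no Week 16 dispensing, so that later off-treatment values do not enter Week 16.

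The cost is a few SAP lines. Week 2 NRS4 rates fall slightly in any arm with responders among its early withdrawals. No continuing subject loses a Week 2 value.

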Appendix 3. A Logistic-Normal GLMM for Longitudinal Binary Data and Tipping Point Analysis

Let Y_{ij} be the binary outcome for subject i ($i = 1, 2, \dots, N$) and visit j ($j = 1, 2, 3, 4, 5$). We assume $Y_{ij} = 1$ for a response and $Y_{ij} = 0$ for a non-response. Then we model as

$$P(Y_{ij} = 1 | x_{ij}, u_i) = \frac{e^{\beta' x_{ij} + u_i}}{1 + e^{\beta' x_{ij} + u_i}} \equiv \pi_{ij}(\beta; u_i)$$

Here, β is a vector of unknown parameters corresponding to the vector of fixed effects x_{ij} and u_i is a subject-specific random effect which is assumed to be normally distributed with mean 0 and variance σ^2 . Note that conditional on u_i , Y_{ij} is independent of Y_{ik} , when $j \neq k$.

The full marginal likelihood of the data is then,

$$L(\beta, \sigma^2) = \prod_{i=1}^N \int_{-\infty}^{\infty} \prod_{j=1}^5 \pi_{ij}(\beta; u_i)^{Y_{ij}} (1 - \pi_{ij}(\beta; u_i))^{(1-Y_{ij})} \times N(u_i; 0, \sigma^2) du_i$$

There is no closed analytical form for this likelihood.

For the present study, the primary endpoint is evaluated at Week 12 ($j = 4$). There are four treatment groups, so the model term $\beta' x_{ij}$ when written out looks like,

$$\beta_0 + \sum_{k=1}^4 \beta_{1k} \times 1_{(T_i=k)} + \beta_{2j} + \sum_{k=1}^4 \beta_{3jk} \times 1_{(T_i=k)}$$

Here, T_i represents treatment for subject i . The third term in the expression is the effect for visit j and the fourth term in the expression is the interaction effect between treatment and visit. With an overall intercept term, the model is over-parameterized as written and so to fit the model, some restrictions on β are required. The default option in many standard statistical software is to assume $\beta_{14} = 0, \beta_{25} = 0$, thereby interpreting β_{11}, β_{12} as the difference in treatment effect relative to $T = 4$ and $\beta_{21}, \beta_{22}, \beta_{23}$ as the difference in visit effect relative to $V = 5$. Consequently, $\beta_{3jk} = 0$ when $j = 5$ or $k = 4$. So, for example, for a subject taking PF-04965842 100 mg QD at Week 12, the expression would be $\beta_0 + \beta_{11} + \beta_{24} + \beta_{341}$. For a subject taking PF-04965842 200 mg QD at Week 12, the expression would be $\beta_0 + \beta_{12} + \beta_{24} + \beta_{342}$. For a subject taking dupilumab at Week 12, the expression would be $\beta_0 + \beta_{13} + \beta_{24} + \beta_{343}$. For a subject on placebo at Week 12, the expression would be $\beta_0 + \beta_{24}$.

Tipping Point Analysis

A method to analyze the longitudinal data of a binary endpoint measured during the placebo-controlled period (eg, IGA and EASI-75 response rates at Weeks 2, 4, 8, 12 and 16) under the MNAR assumption is called the tipping point analysis. This tipping point analysis

includes two popular scenarios as special cases: (1) the Jump-to-Reference (JTR) analysis in which the response rate for a missing subject assessment in the active treatment group takes on (ie, jumps to) the rate for the reference or control treatment group and (2) the MAR analysis in which the response rate for a missing subject assessment in each treatment group is based on the posterior predictive response rate for that treatment group alone.

The saturated logit-normal GLMM as described above will be used as the imputation model. Estimation of the model parameters will be performed under the Bayesian framework using Markov Chain Monte Carlo (MCMC) methods. We assign a non-informative prior for each component of β to be independent and identically distributed as $\sim N(0, 10000)$ and assign a weakly informative prior for σ^2 as an Inverse-Gamma distribution with shape=1 and scale=1. With this prior distribution, the 90th percentile for σ^2 is approximately 9.

Let $\beta^b, u_i^b, b = 1, 2, \dots, B$ be a sample from the posterior distribution. A single imputation $\widetilde{Y}_{i,j}^b$ of missing Y_{ij} is based on the posterior predictive distribution of the response probabilities estimated from the GLMM. For example, if subject i is randomized to PF-04965842 100 mg QD ($T_i = 1$), then at Week 12 ($V = 4$),

$$\text{logit}(\pi_{i,1,4}^b) = \text{logit} \left(P \left(\widetilde{Y}_{i,4}^b = 1 \mid T_i = 1, V = 4 \right) \right) = \beta_0^b + \beta_{11}^b + \beta_{24}^b + \beta_{341}^b + u_i^b.$$

If subject i is randomized to PF-04965842 200 mg QD ($T_i = 2$), then at Week 12 ($V = 4$),

$$\text{logit}(\pi_{i,2,4}^b) = \text{logit} \left(P \left(\widetilde{Y}_{i,4}^b = 1 \mid T_i = 2, V = 4 \right) \right) = \beta_0^b + \beta_{12}^b + \beta_{24}^b + \beta_{342}^b + u_i^b.$$

If subject i is randomized to dupilumab ($T_i = 3$), then at Week 12 ($V = 4$),

$$\text{logit}(\pi_{i,3,4}^b) = \text{logit} \left(P \left(\widetilde{Y}_{i,4}^b = 1 \mid T_i = 3, V = 4 \right) \right) = \beta_0^b + \beta_{13}^b + \beta_{24}^b + \beta_{343}^b + u_i^b.$$

If subject i is randomized to placebo ($T_i = 4$), then at Week 12 ($V = 4$),

$$\text{logit}(\pi_{i,4,4}^b) = \text{logit} \left(P \left(\widetilde{Y}_{i,4}^b = 1 \mid T_i = 4, V = 4 \right) \right) = \beta_0^b + \beta_{24}^b + u_i^b.$$

In the tipping analysis, we apply a series of fixed quantities $\delta = (\delta_1, \delta_2, \delta_3)'$ to account for MNAR. We define,

$$\begin{aligned} \pi_{i,4,4}^{*b} &= \pi_{i,4,4}^b, \\ \pi_{i,1,4}^{*b} &= \delta_1 \pi_{i,4,4}^b + (1 - \delta_1) \pi_{i,1,4}^b, \\ \pi_{i,2,4}^{*b} &= \delta_2 \pi_{i,4,4}^b + (1 - \delta_2) \pi_{i,2,4}^b, \\ \pi_{i,3,4}^{*b} &= \delta_3 \pi_{i,4,4}^b + (1 - \delta_3) \pi_{i,3,4}^b \end{aligned}$$

We then sample the single imputed value $\widetilde{Y}_{i,j}^b$ from a Bernoulli distribution with probability of success $\pi_{i,T_i,4}^{*b}$. For the present analysis, the responses from the placebo arm are not shifted.

Analysis of an imputed data set will produce an estimate as well as standard error of the treatment difference using CMH and normal approximation in [Section 5.2.1](#). For a given value of MNAR parameter δ , this is repeated for B (typically, $B=500$) times to generate B complete imputed data sets and these B sets of estimates are combined using the Rubin's Method (Rubin, 1987). This can then be repeated for different values of MNAR parameter δ to evaluate the impact of missing data. Note that $\delta = (0, 0, 0)'$ corresponds to an MAR analysis and $\delta = (1, 1, 1)'$ corresponds to an analysis commonly known as Jump-To-Reference (JTR). As a special case, we will consider $\delta_1 = \delta_2 = \delta_3$ for our analyses.

The multiple imputations will be done for all treatment groups. Only PF-04965842 200 mg QD, PF-04965842 100 mg QD and placebo results will be presented in Tipping Point Analysis to support the family-wise type one error controlled comparisons of the primary endpoints.

Appendix 4. Investigator’s Global Assessment (IGA)

The Investigator’s Global Assessment of atopic dermatitis is scored on a 5-point scale (0-4), reflecting a global consideration of the erythema, induration and scaling. The clinical evaluator of atopic dermatitis will perform an assessment of the overall severity of atopic dermatitis and assign an IGA score and category as described in the table below. The assessment will be a static evaluation without regard to the score at a previous visit.

IGA Score

Score	Category	Description*
0	Clear	Atopic dermatitis is cleared, except for any residual discoloration (post-inflammatory hyperpigmentation and/or hypopigmentation).
1	Almost Clear	Overall, the atopic dermatitis is not entirely cleared and remaining lesions are light pink (not including post inflammatory hyperpigmentation) and/or; have barely palpable hard thickened skin and/or papules and/or; have barely perceptible lichenification; excoriation and oozing/crusting are absent.
2	Mild	Overall, the atopic dermatitis consists of lesions that are light red; with slight, but definite hard thickened skin and/or papules; with slight, but definite linear or picked scratch marks or penetrating surface injury; with slight, but definite thickened skin, fine skin markings, and lichenoid scale; oozing/crusting is absent.
3	Moderate	Overall, the atopic dermatitis consists of lesions that are red; with easily palpable moderate hard thickened skin and/or papules; with moderate linear or picked scratch marks or penetrating surface injury; with moderate thickened skin, coarse skin markings, and coarse lichenoid scale; with slight oozing/crusting.
4	Severe	Overall, the atopic dermatitis consists of lesions that are deep, dark red; with severe hard thickened skin and/or papules; with severe linear or picked scratch marks or penetrating surface injury; with severe thickened skin with very coarse skin markings and lichenoid scale; with moderate to severe oozing/crusting.

* The IGA will exclude scalp, palms, and soles from the assessment/scoring.

090177e1937d0b4e\Approved\Approved On: 18-May-2020 15:17 (GMT)

Appendix 5. Eczema Area and Severity Index (EASI)

The EASI quantifies the severity of a subject’s atopic dermatitis based on both severity of lesion clinical signs and the percent of BSA affected. EASI is a composite scoring by the atopic dermatitis clinical evaluator of the degree of erythema, induration/papulation, excoriation, and lichenification (each scored separately) for each of four body regions, with adjustment for the percent of BSA involved for each body region and for the proportion of the body region to the whole body.

Lesion Severity by Clinical Signs: The basic characteristics of atopic dermatitis lesions-erythema, induration/papulation, excoriation, and lichenification-provide a means for assessing the severity of lesions. Assessment of these four main clinical signs is performed separately for four body regions: head and neck, upper limbs, trunk (including axillae and groin) and lower limbs (including buttocks). Average erythema, induration/papulation, excoriation, and lichenification are scored for each body region according to a 4-point scale: 0=absent; 1=mild; 2=moderate; 3=severe. Morphologic descriptors for each clinical sign severity score are shown in the table below.

Clinical Sign Severity Scoring Criteria for the EASI

Score		Description*
Erythema (E)		
0	Absent	None; may have residual discoloration (post-inflammatory hyperpigmentation and/or hypopigmentation).
1	Mild	Light pink to light red
2	Moderate	Red
3	Severe	Deep, dark red
Induration/Papulation (I)		
0	Absent	None
1	Mild	Barely palpable to slight, but definite hard thickened skin and/or papules
2	Moderate	Easily palpable moderate hard thickened skin and/or papules
3	Severe	Severe hard thickened skin and/or papules
Excoriation (Ex)		
0	Absent	None
1	Mild	Slight, but definite linear or picked scratch marks or penetrating surface injury
2	Moderate	Moderate linear or picked scratch marks or penetrating surface injury
3	Severe	Severe linear or picked scratch marks or penetrating surface injury
Lichenification (L)		
0	Absent	None
1	Mild	Barely perceptible to slight, but definite thickened skin, fine skin markings, and lichenoid scale
2	Moderate	Moderate thickened skin, coarse skin markings, and coarse lichenoid scale
3	Severe	Severe thickened skin with very coarse skin markings and lichenoid scale

* The EASI will exclude scalp, palms, and soles from the assessment/scoring.

%BSA with Atopic Dermatitis: The number of handprints of skin afflicted with atopic dermatitis in a body region can be used to determine the extent (%) to which a body region is involved with atopic dermatitis (see table below). When measuring, the handprint unit refers to the size of each individual subject’s hand with fingers in a closed position.

090177e1937d0b4eApproved\Approved On: 18-May-2020 15:17 (GMT)

Handprint Determination of %BSA

Body Region	Total Number of Handprints in Body Region*	Surface Area of Body Region Equivalent of One Handprint*
Head and Neck	10	10%
Upper Limbs	20	5%
Trunk (including axillae and groin/genitals)	30	3.33%
Lower Limbs (including buttocks)	40	2.5%

Handprint refers to the hand size of each individual subject.

* The number of handprints will be for the entire body region; these values will not be adjusted for exclusion of scalp, palms, and soles from the BSA assessment.

EASI Area Score Criteria

Percent BSA with Atopic Dermatitis in a Body Region	Area Score
0%	0
>0 - <10%	1
10 - <30%	2
30 - <50%	3
50 - <70%	4
70 - <90%	5
90 - 100%	6

Body Region Weighting: Each body region is weighted according to its approximate percentage of the whole body (see table below).

EASI Body Region Weighting

Body Region	Body Region Weighting
Head and Neck	0.1
Upper Limbs	0.2
Trunk (including axillae and groin/genitals)	0.3
Lower Limbs (including buttocks)	0.4

* No adjustment for body regions excluded for assessment

In each body region, the sum of the Clinical Signs Severity Scores for erythema, induration/papulation, excoriation, and lichenification is multiplied by the Area Score and by the Body Region Weighting to provide a body region value, which is then summed across all four body regions resulting in an EASI score as described in Equation below.

$$EASI = 0.1Ah(Eh+Ih+Exh+Lh) + 0.2Au(Eu+Iu+ExU+Lu) + 0.3At(Et+It+Ext+Lt) + 0.4Al(EI+II+ExI+LI)$$

A = Area Score; E = erythema; I = induration/papulation; Ex = excoriation;
L = lichenification; h = head and neck; u = upper limbs; t = trunk; l = lower limbs

The EASI score can vary in increments of 0.1 and range from 0.0 to 72.0, with higher scores representing greater severity of atopic dermatitis.

